10.1 Cumulative-failure-time-based parameters of interest

Let T be the failure time using the study time scale (based on one of the study time origins defined above), t_0 a fixed time point of interest after the given time origin, and W baseline covariates. For a given analysis, we denote by A a binary indicator of belonging to either of strata which define the comparison groups of interest. In the primary analysis A is indicator of receiving a bivalent or monovalent M6 booster (in analyses), and it is similarly defined elsewhere. We denote by $T(a)$ the counterfactual failure time if $A = a$.

In a cumulative-incidence-based analysis, parameters of interest are the marginalized failure time

Comparing bivalent vs. monovalent booster		
Exploratory analysis I		
Target population	FAS participants receiving a M6 vaccine regardless of randomization scheme (FM6)	
Endpoint	COVE-/CDC-based/Severe (when applicable) COVID-19 endpoints counted 1 day after M6 vaccination	
Time frame	M6 vaccination to M12/M18 visit	
Exploratory analysis II		
Target population	FAS PLWH/PLWoH receiving a M6 vaccine regardless of randomization scheme (FM6)	
Endpoint	COVE-/CDC-based/Severe (when applicable) COVID-19 endpoints counted 1 day after M6 vaccination	
Time frame	M6 vaccination to M12/M18 visit	
Comparing baseline hybrid vs. vaccine immunity among PLWH		
Exploratory analysis III		
Target population	AG1 and AG2.1 receiving a bivalent M6 vaccine regardless of randomization scheme (AG1 and AG2.1 in FM6)	
Endpoint	COVE-/CDC-based/Severe (when applicable) COVID-19 endpoints counted 1 day after enrollment	
Time frame	Enrollment to M12/M18 visit	
Exploratory analysis IV		
Target population	AG1 and AG2.1 receiving a monovalent M6 vaccine regardless of randomization scheme (AG1 and AG2.1 in FM6)	
Endpoint	COVE-/CDC-based/Severe (when applicable) COVID-19 endpoints counted 1 day after enrollment	
Time frame	Enrollment to M12/M18 visit	
Exploratory analysis V		
Target population	AG1 and AG2.1 not receiving M6 vaccination regardless of randomization scheme (AG1 and AG2.1 in FM6)	
Endpoint	COVE-/CDC-based/Severe (when applicable) COVID-19 endpoints counted 1 day after enrollment	
Time frame	Enrollment to M12/M18 visit	
Comparing Month 6 hybrid vs. vaccine immunity among PLWH		
Exploratory analysis VI		
Target population	AG1 and AG2.1 receiving a monovalent M6 vaccine regardless of randomization scheme (AG1 and AG2.1 in FM6)	
Endpoint	COVE-/CDC-based/Severe (when applicable) COVID-19 endpoints counted 14 day after M6 vaccination	
Time frame	13 days post M6 vaccination to M12/M18 visit	
Exploratory analysis VII		
Target population	AG1 and AG2.1 receiving a bivalent M6 vaccine regardless of randomization scheme (AG1 and AG2.1 in FM6)	
Endpoint	COVE-/CDC-based/Severe (when applicable) COVID-19 endpoints counted 14 day after M6 vaccination	
Time frame	13 days post M6 vaccination to M12/M18 visit	

Table 3: Summary of target population and study endpoints for exploratory analyses

cumulative distribution functions $E_W[P(T \leq t_0 | A = a, W)]$ over a range of fixed time points t_0 , and the contrasts $\theta^{\text{diff}}(t_0) = E_W[P(T \leq t_0 | A = 1, W)] - E_W[P(T \leq t_0 | A = 0, W)]$ and $\theta^{rr}(t_0) = E_W[P(T \leq t_0 | A = 1, W)]/E_W[P(T \leq t_0 | A = 0, W)]$. When the treatment assignment A is randomized, e.g., in Primary Analysis I of the randomized cohort RM6, the statistical parameter $E_W[P(T \leq t_0 | A = a, W)]$ coincides with the causal parameter $E_W[P(T(a) \leq t_0 | W)]$ and is the ultimate estimand of interest. In exploratory analyses involving non-randomized comparison groups (i.e., exploratory analyses I, II, and III in Table 3), the statistical parameter $E_W[P(T \leq t_0 | A = a, W)]$ equals the causal parameter $E_W[P(T(a) \leq t_0 | W)]$ under standard causal identification assumptions, and $\theta^{\text{diff}}(t_0)$ and $\theta^{rr}(t_0)$ are two versions of an average treatment effect.

Even if the causal assumptions fail, the parameter $E_W[P(T \leq t_0 | A = a, W)]$ may still be of greater scientific interest than the unadjusted survival probability. The first reason for this is that this parameter allows for the adjustment of covariates related to both A and T . As a result, this parameter can be interpreted as the average probability that $T \leq t_0$ in a hypothetical population of participants with $A = a$ but with a distribution of the covariate vector W identical to that in the target population. The second reason is that adjusting for W allows the relaxation of the marginal independent censoring assumption $T(a) \perp C(a)|A$ to a conditional independent censoring assumption $T(a) \perp C(a)|A, W$. This relaxation can be important in contexts where the event and censoring times may be dependent, but the recorded covariate vector W at least partly explains the dependence between them.

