needed for the number of participants randomized were generated in the treatment table and treatment keys. Participants receiving their Month 6 vaccination under Version 6 were blinded to their assignment to either the monovalent or bivalent vaccine. Participants who received Month 6 vaccination prior to Version 6 were not subject to this randomization. The randomization was done in blocks to ensure balance within each study group among participants who received their Month 6 vaccination under Version 6. More details can be found in a separate blinding management plan (Version 8.0) accessible only to unblinded statisticians prior to the unblinding of the study.

3 Analysis cohorts

The following analysis cohorts will be considered:

- Randomized Month 6 cohort (RM6): this cohort is the primary Part B post-M6 stage analysis cohort, and it includes all FAS participants who received a Month 6 vaccination under the randomization scheme.
- Full Month 6 cohort (FM6): this cohort is the exploratory Part B post-M6 stage analysis cohort, and it includes all FAS participants who received a Month 6 vaccination, regardless of in or outside of the randomization scheme.
- Full per-protocol cohort (FPP): this cohort is the primary Part A+B combined analysis cohort, and it includes all participants who received their M0, M1 (if applicable) and M6 vaccinations as assigned without major protocol violations. All participants in this cohort should have received their Month 6 vaccination according to the randomization scheme.
- Full Analysis Set (FAS): this cohort is the exploratory Part A+B combined analysis cohort, and it includes all participants who enrolled into the study (excluding 235 participants from one site due to data quality concerns).

4 Time-to-event endpoints

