For this exploratory analysis of COVID-19 and severe COVID-19 between baseline hybrid vs. vaccine immunity groups using the first definition described above, the same analysis will be repeated for three subsets of participants: 1) participants who received the monovalent Month 6 booster; 2) participants who received the bivalent Month 6 booster; and 3) participants who did not receive the Month 6 vaccination. An analysis will be performed only if there are at least 7 endpoints in a given subset of participants. These analyses seek to understand if participants' COVID-19 and severe COVID-19 risk differs between baseline hybrid and vaccine immunity groups, counting events starting 1 day after enrollment till Month 12 or Month 18 (as opposed to Month 6 in the Part A analyses). All covariates considered in the Part A analyses of hybrid vs. vaccine immunity will be considered. In addition, Month 6 vaccination will be included as a time-varying covariate using the Cox model approach. The cumulative incidence approach will not be considered for these exploratory analyses.

Comparing Month 6 hybrid vs. vaccine immunity groups among PLWH

For this exploratory analysis of COVID-19 and severe COVID-19 between Month 6 hybrid vs. vaccine immunity groups based on the 2nd definition described above, the same analysis will be repeated for two subsets of participants: 1) participants who received the monovalent Month 6 booster; and, 2) participants who received the bivalent Month 6 booster. An analysis will be performed only if there are at least 7 endpoints in a given subset of participants. These analyses seek to understand if participants' COVID-19 and severe COVID-19 risk after the Month 6 vaccination differs between hybrid and vaccine immunity groups defined at Month 6, counting events starting 14 days after the Month 6 vaccination date. All covariates considered in the Part A analyses of hybrid vs. vaccine immunity will be considered, except that the covariate values are defined at Month 6 whenever applicable. Only the Cox model approach will be considered for these analyses; the cumulative incidence approach will not be considered.

9 Summary of primary, secondary and exploratory analyses

Table 2 summarizes the target population, study endpoints, and time frame for various primary and secondary analyses. Table 3 further summarizes the same information for various exploratory

analyses.

	Primary analysis I (applicable when # COVID-19 endpoints is at least 20)

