11.4.3 Exploratory comparisons

Exploratory analysis I is analogous to primary analysis I and secondary analysis I except that the analysis cohort will be the full M6 cohort (FM6). The same stratification and covariate adjustment strategies used in secondary analysis I will be adopted here.

Exploratory analysis II is analogous to the secondary analysis III except that the analysis cohort will be the FM6 PLWH/PLWoH. The same stratification and covariate adjustment strategies used in secondary analysis III will be adopted here.

Exploratory analysis III seeks to compare the COVID-19 incidence among participants in Analysis Group 1 vs. Analysis Group 2-1 (defined at baseline/enrollment) counting events from enrollment. To this end, the following Cox regression model is considered:

$$\lambda_{ji}(t | A_i, W_i) = \lambda_{0j}(t) \exp \{ \beta A_i + \beta_1 Z_i(t) + \beta_2 A_i Z_i(t) + \gamma^T W_i \} I(t > \tau_i^{\text{enroll}}), \quad (6)$$

with $A_i = 1$ if participant i is in AG 2-1 and 0 if in AG 1, and $Z_i(t)$ is a time-varying indicator of receiving a M6 booster vaccine. The analysis will consider the same stratification and covariate adjustment strategy as specified in the pre-M6 SAP. Key parameters of interest include $\exp\{\beta\}$, $\exp\{\beta_1\}$ and $\exp\{\beta_2\}$.

Exploratory analysis IV and V are analogous to exploratory analysis III and will adopt the same stratification and covariate adjustment strategies.

Exploratory analysis VI and VII are analogous to the hybrid vs. vaccine-induced comparison as specified in the pre-M6 SAP, except that the analysis will define the hybrid vs. vaccine immunity status based on M6 and count events 13 days post M6 vaccination. The analyses will adopt the same stratification and covariate adjustment strategies as its pre-M6 counterpart.

12 Multiplicity adjustment

For all analyses, point estimates, 95% CIs and nominal p-values will be displayed in forest plots without multiplicity adjustment. No multiple hypothesis testing will be done in any described analyses.

13 Handling missing data

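### Exploratory analysis V names an empty cohort and two parameters it cannot estimate, and III–V count events from enrolment in subsets defined by later receipt or non-receipt of the Month 6 dose

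*SAP*

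**What the plan says.** SAP Section 3 defines the Full Month 6 cohort (FM6): "it includes all FAS participants who received a Month 6 vaccination, regardless of in or outside of the randomization scheme". Table 3 then sets the populations of three exploratory comparisons of baseline hybrid immunity (AG2.1) with vaccine immunity (AG1) among people living with HIV:

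- III: "AG1 and AG2.1 receiving a bivalent M6 vaccine regardless of randomization scheme (AG1 and AG2.1 in FM6"
- IV: "AG1 and AG2.1 receiving a monovalent M6 vaccine regardless of randomization scheme (AG1 and AG2.1 in FM6"
- V: "AG1 and AG2.1 not receiving M6 vaccination regardless of randomization scheme (AG1 and AG2.1 in FM6"

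All three share one endpoint line, "COVE-/CDC-based/Severe (when applicable) COVID-19 endpoints counted 1 day after enrollment", and Section 8.2.2 agrees: "counting events starting 1 day after enrollment till Month 12 or Month 18".

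Section 11.4.3 gives model (6) for III, with linear predictor βA + β1Z(t) + β2A·Z(t) + γᵀW. A is 1 for AG2.1 and 0 for AG1, and Z(t) "is a time-varying indicator of receiving a M6 booster vaccine". It lists exp(β), exp(β1) and exp(β2) as key parameters. For the other two: "Exploratory analysis IV and V are analogous to exploratory analysis III and will adopt the same stratification and covariate adjustment strategies". No reduced model is given for V, and Section 8.2.2 also attaches the time-varying Month 6 term to all three subsets.

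Elsewhere the SAP describes V differently. Section 1 says that the exploratory work takes in people without the Month 6 boost. Section 8.2 draws the hybrid-versus-vaccine comparison from everyone enrolled, with no booster as one category. Section 8.2.2 lists non-recipients as its third subset without restricting it to FM6.

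**The concern.** There are three separate difficulties. A programmer working from Table 3 would find no participants for V. One who repaired the cohort from the text would then meet two declared key parameters that the data cannot inform. In all three analyses the clock starts at enrolment, while membership depends on something that happens, or does not, about six months later. In III and IV a person with COVID-19 before Month 6 counts as a case only if later dosed. Anyone who died, was lost, or took an outside vaccine before the dose is left out, rather than contributing time until censoring under Section 4. The SAP neither discusses nor corrects for this.

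At stake are the reported change in hazard after the booster, exp(β1); its difference between immunity groups, exp(β2); and, in some circumstances, the hybrid-versus-vaccine contrast itself.

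**Working it through.** The documents state no event count, power or sample size for III–V, so there is no figure to reproduce.

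**1. Cohort of V.** FM6 requires a Month 6 dose and V requires none. The intersection is 0 participants.

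**2. Model (6) in V after repair.** Take AG1 and AG2.1 non-recipients from the Full Analysis Set (FAS). Z(t) = 0 for all of them at all times, so A·Z(t) = 0 too, and the predictor reduces to βA + γᵀW. In a simulated data set the design for (A, Z, A·Z) had rank 1 of 3, and the information matrix was zero in every entry for β1 and β2. Only β is estimable.

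**3. Model (6) in III and IV.** Z(t) switches from 0 to 1 at the dose. The rank was 3 of 3 and the information matrix positive definite, so both can be fitted.

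**4. Effect of selecting on a later dose (III–IV).** For group g let k_g = P(dose | case before Month 6) / P(dose | no case before Month 6). With rare events, the pre-dose rate among the dosed is multiplied by about k_g; the post-dose rate is unchanged, because those at risk then were not earlier cases. Hence:

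- observed exp(β) = true × k_AG2.1 / k_AG1
- observed exp(β1) = true × 1 / k_AG1
- observed exp(β2) = true × k_AG1 / k_AG2.1

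For receipt of 0.80 against 0.95, k = 0.842 and 1/k = 1.188. For 0.50 against 0.95, k = 0.526 and 1/k = 1.90.

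This was checked by person-time simulation with 4 million participants. The rates were the annual incidences in Protocol Section 2.1, 7.1% vaccine-only and 2.2% hybrid (ratio 0.31). Hazards were constant, with true exp(β1) = exp(β2) = 1. The receipt probabilities are assumptions; the documents give none.

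| P(dose): AG1 cases / AG2.1 cases / non-cases | exp(β), true 0.31 | exp(β1), true 1 | exp(β2), true 1 |
|---|---|---|---|
| 0.95 / 0.95 / 0.95 | 0.309 | 0.990 | 1.006 |
| 0.80 / 0.80 / 0.95 | 0.311 | 1.176 | 0.992 |
| 0.50 / 0.50 / 0.95 | 0.312 | 1.912 | 1.001 |
| 0.80 / 0.95 / 0.95 | 0.372 | 1.183 | 0.841 |
| 0.95 / 0.80 / 0.95 | 0.262 | 0.995 | 1.195 |

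Calendar-time Cox fits for rows 1, 2 and 4, at higher incidence (0.25 and 0.08 per year), agreed with the formulas within two Monte Carlo standard errors.

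**5. The same issue in V.** Selection is on non-receipt. At 0.80 against 0.95 the ratio for the pre-Month 6 rate is 0.20/0.05 = 4. As in III–IV, exp(β) is distorted only if this ratio differs between AG1 and AG2.1. This step is arithmetic only and was not simulated.

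**6. Would V have data once repaired?** Enrolled 14,237, less 235 from the excluded site (SAP Sections 2 and 3), times about 80% living with HIV (Protocol Section 2.1.1), is about 11,200. Protocol Section 6.3.1 plans for 5% missing any dose: 11,200 × 0.05 = 560. With a 1:2 group split, events over Months 0–6 are 560 × (0.071/3 + 0.022 × 2/3) × 0.5 = 10.7, or about 21 over Months 0–12 if all are followed. At 2% to 20% missing, the ranges are 224 to 2,240 people, 4 to 43 events and 9 to 86 events. These are generous: AG1 excludes point-of-care negatives who were positive on another test, and many non-recipients will have left early. The Section 8.2.2 minimum of 7 endpoints could still be met.

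**The case against.** The case for leaving this alone has four parts.

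- V's empty cohort is a wrong tag in one table cell, and the SAP text shows what was meant.
- Section 8.2.2 asks whether risk differs between hybrid and vaccine immunity. That is β, which is estimable in all three analyses and unbiased in III–IV when any link between illness and dosing is the same in both groups (table, rows 2 and 3).
- The documents do not say that cases forgo the Month 6 dose. Protocol Section 9.9 delays vaccination until recovery, so most cases may still be dosed, and with no dependence there is no bias. Z(t) is also time-varying, so pre-dose time is not credited to the booster.
- The analyses are exploratory, need at least 7 endpoints each, and Section 8.2 says they may not all be done for the primary publication.

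Most of this stands, and it rules out some stronger readings. A reader might infer that none of III–V can be run; III and IV can. A reader might infer that exp(β1) is biased by construction, or in a known direction; that needs dose receipt to depend on earlier COVID-19, which the documents do not establish. A reader might also take III–V to be the only hybrid-versus-vaccine comparisons to Month 18; VI and VII make it too, starting after the Month 6 dose.

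What does not fall is that exp(β1) and exp(β2) are declared key parameters. They do not exist in V, and in III–IV they rest on an unstated assumption that dosing is unrelated to earlier COVID-19. Some link is plausible: illness delays vaccination (Protocol Section 9.9), and an outside COVID-19 vaccine ends study vaccination (Protocol Section 9.10).

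**Conclusion.** The point holds in three parts, with different certainty.

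- Certain from the text: V's Table 3 population is empty and contradicts SAP Sections 1, 8.2 and 8.2.2.
- Certain from the algebra: in the intended V cohort exp(β1) and exp(β2) cannot be estimated; exp(β) can.
- Conditional: in III–IV, exp(β1) is biased if AG1 members with COVID-19 before Month 6 are more or less likely to be dosed than those without. Over the assumed range, with both groups affected alike, it runs from about 1.0 to 1.9 when the truth is 1. exp(β) and exp(β2) are biased only if that link differs between AG1 and AG2.1; with one group affected at 0.80 against 0.95, exp(β) moves from 0.31 to 0.37 or 0.26. V carries the mirror-image selection on non-receipt.

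The sizes rest on assumed receipt probabilities and constant hazards. The primary and secondary analyses and Exploratory VI–VII count from the Month 6 dose and are untouched. This should be corrected, but it does not threaten the trial's main conclusions.

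**What to change.** 1. In Table 3, change V's cohort to AG1 and AG2.1 members of the FAS who did not receive the Month 6 dose.
2. Replace III–V by one calendar-time Cox model in all AG1 and AG2.1 participants of the FAS. Give Z(t) three levels (none, monovalent, bivalent): everyone starts at none and switches on the date of the Month 6 dose. Include its interaction with immunity group, and report the hybrid-versus-vaccine hazard ratio at each level. Membership then uses no future information, as Section 8.2's reference to all enrolled participants implies.
3. If V is kept as a separate analysis, drop Z and A·Z, report exp(β) only, and state that the subset is selected on later non-receipt.
4. Reconcile Section 10.3, which ends calendar-time Cox follow-up at the Month 6 vaccination, with the Month 12/Month 18 time frame in Table 3. Taken literally, Z(t) would never switch on in the new model either.

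The cost is SAP wording and one model in place of three; no new data are needed. There are two downsides. Covariate effects are shared across booster levels. And the none level mixes everyone's pre-dose time with non-recipients' later time, so non-recipients are no longer examined on their own unless V is kept under item 3.

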10.2 Selection of the final time point t_0

For analyses using study enrolment as the time origin, and for a given group comparison, the fixed time point t_0 is chosen to be minimum of 365 (or 540) days and the latest possible time point when stable estimation using follow-up data through the Month 12 (or Month 18) visit can be reasonably assured. For analyses using 13 days after the Month 6 vaccination as the time origin, and for a given group comparison, the fixed time point t_0 is chosen to be minimum of 165 (or 365) days and the latest possible time point when stable estimation using follow-up data through the Month 12 or Month 18 study visit can be reasonably assured. Identifying the minimum t_0 for which stable estimation can be assured is operationalized by selecting the latest point for which the standard error for the log risk ratio satisfies

$$\left| \frac{\log(3)}{\widehat{SE}(t)} \right| \geq z^{1-\alpha/2},$$

where $\widehat{SE}(t)$ denotes the estimated standard error for the log of the cumulative risk ratio at time t and $z^{1-\alpha/2}$ is the $1 - \alpha/2$ quantile of the standard normal distribution. The rationale is we would only consider an estimate valuable if we have enough precision to conclude that a large cumulative risk ratio (of size 3.0 or larger) is statistically significant at the level α . Study participants with an endpoint observed after t_0 are considered to have censored outcomes.

It is expected that, for analyses using the severe COVID-19 endpoint, the standard error may be very large for all time points due to a low event rate. Therefore, for analyses using study enrolment as the time origin, the time point t_0 is fixed at 365 (or 540) days for analyses through Month 12 (or Month 18), and for analyses using 13 days after the Month 6 vaccination as the time origin, t_0 is chosen to be 165 (or 365) days for analyses through Month 12 (or Month 18). That is, no data-adaptive selection of t_0 is performed when using the severe COVID-19 endpoint.

10.3 Cox-regression-based parameters of interest

We consider parameters of interest defined under the assumption of a proportional hazards model on a calendar time scale. Cox regression allows for flexible nonparametric modeling of the baseline hazard as a function of calendar time, acknowledging that the COVID-19 epidemic undergoes unpredictable changes over calendar time.

Suppose there are J baseline strata, $j = 1, \dots, J$. The proportional hazards model can be written as

$$\lambda_j(t | A, W) = \lambda_{0j}(t) \exp \{ \beta A + \gamma^T W \} \quad (1)$$

for a binary treatment assignment A . In addition to the parameter β in Model (1), parameters γ of variables like an indicator of having an infection during Part A of the study (see Section 7.1 for details) or CD4 counts/viral load will be reported in case they are of interest.

The β coefficients for the calendar-time-based Cox models are the coefficients for which results are reported; results for the β coefficients for the study time Cox modeling are not reported, to avoid too many results and potential confusion. Therefore, the use of the Cox model on the study/enrolment

time scale is solely as an intermediate step in covariate-adjusted cumulative incidence estimation, given that the cumulative incidence results use study/enrolment time.

For cumulative incidence based analyses discussed in Section 10.1, a final time point t_0 was selected and failure times beyond t_0 were right-censored at t_0 . The calendar-time Cox models do not use this fixed value of t_0 ; rather calendar-time Cox models consider all follow-up up through the M6 vaccination, subject to right-censoring described in Section 4.

11 Statistical methods for estimation/inference

